4.2.2.2 Immune-Related Adverse Events (IRAEs)

Blocking PD-1 and CCR2/5 functions may permit the emergence of auto-reactive T-cells and resultant clinical autoimmunity. IRAE may occur in the following categories: gastrointestinal, renal pulmonary, hepatic, endocrinopathies, skin and neurological.

For the purposes of this study, an IRAE is defined as an AE of unknown etiology, associated with drug exposure and is consistent with an immune phenomenon. Efforts should be made to rule out neoplastic, infectious, metabolic, toxin or other etiologic causes prior to labeling an AE an IRAE. Serological, immunological, and histological (biopsy) data should be used to support the diagnosis of an immune-mediated toxicity. Suspected IRAEs must be documented on an AE or SAE Case Report Form (CRF).

4.3 Prohibited and Restricted Therapies

Medications taken within 4 weeks prior to study treatment administration must be recorded.

4.3.1 Patients may not use any of the following agents during the study:

- In vitro, the metabolism of BMS-813160 was primarily mediated via cytochrome P450 (CYP) 3A4, with some contribution from CYP3A5, and BMS-813160 was also a substrate for P-glycoprotein (P-gp). Based on these results, the potential exists for drug-drug interactions if BMS-813160 is co-administered with inhibitors or inducers of CYP3A4 or P-gp. Therefore use of any strong inhibitors or inducers of CYP3A4 or P-gp is not allowed (see **Appendix C**).
- Grapefruit and Seville oranges and their juices can inhibit CYP3A4 and should not be consumed while on study.

A Phase I/II trial of combination immunotherapy with nivolumab and a CCR2/CCR5 dual antagonist (BMS-813160) with or without GVAX following chemotherapy and radiotherapy for locally advanced pancreatic ductal adenocarcinomas (PDACs)

- Class I antiarrhythmics (eg, quinidine, procainamide, disopyramide, lidocaine, phenytoin, mexiletine, tocainide, flecainide, propafenone, moricizine).
- Any non-study anticancer or immunotherapy agent (investigational or non-investigational).
- Any other investigational agents.
- Any other immunotherapy treatment, including, but not limited to: IL-2, interferon, anti-PD-1, anti-PD-L1, anti-PD-L2, anti-CD137, anti-OX-40, anti-CD40, anti-CCR2/5 or anti-CTLA-4 antibodies.
- Systemically active steroids can be used, but should be reported to the Principal Investigator, BMS and IND Sponsor. Steroid treatment courses that are longer than 4 days should be completed at least 14 days prior to resuming study-related treatments (See **Section 5.1** for dosing delays for steroids).
- Immunosuppressive agents.
- Filgrastim (Neupogen® or G-CSF), sargramostim (Leukine® or GM-CSF), erythropoietin, other growth factors.
- Live vaccines (examples of live vaccines include, but are not limited to: measles, mumps, rubella, chicken pox, yellow fever, rabies, BCG, and typhoid [oral] vaccine). Seasonal influenza vaccines for injection are generally killed virus vaccines and are allowed. However, intranasal influenza vaccines (e.g. Flu-Mist®) are live attenuated vaccines, and are not allowed.
- Tricyclic antidepressants

4.3.2 Caution is warranted in the following situations:

- Caution is warranted with concomitant use of MATE1 substrates with a narrow therapeutic index.
- Caution is warranted when administering BMS-813160 to participants taking drugs that are moderate inhibitors or inducers of CYP3A4. Moderate CYP3A4 modulators (i.e. inhibitor or inducer) are allowed with caution only after the first 4 weeks of receiving combination immunotherapy. See **Appendix C** for a list of CYP3A4 modulators.
- Methadone (in particular at high doses) due to potential sodium channel blockade

4.4 Definition of an Overdose for this Protocol

No cases of overdose have been reported in clinical trials for BMS-813160, nor GVAX pancreas vaccine. In case of overdose, patients should be closely monitored for signs or symptoms of adverse reactions, and appropriate symptomatic treatment instituted immediately. There are no specific antidotes for nivolumab, BMS-813160 nor GVAX pancreas vaccine.

An overdose is defined as the accidental or intentional administration of any dose greater than the assigned dose of study treatment that is considered both excessive and medically important. All occurrences of overdose must be reported as an SAE (see **Section 6.5**).

In the event of an overdose, the Principal Investigator will do the following:

- Contact BMS Worldwide Safety [REDACTED] and IND Sponsor immediately using the SAE Reporting Form in Appendix B.
- Closely monitor the participant for AEs/SAEs and laboratory abnormalities until effects can no longer be detected systemically
- Obtain a plasma sample for PK analysis if requested by BMS or IND Sponsor, or if deemed necessary by the Principal Investigator (determined on a case-by-case basis)
- Document the quantity of the excess dose as well as the duration of the overdosing in the Case Report Form (CRF)

Decisions regarding dose interruptions or modifications will be made by the Principal Investigator in consultation with BMS and/or the IND Sponsor based on the clinical evaluation of the participant.

4.5 Contraception, Use in Pregnancy, Use in Nursing

4.5.1 Contraception

The investigational agents may have adverse effects on a fetus *in utero*. Furthermore, it is not known if the investigational agents have transient adverse effects on the composition of sperm. Non-pregnant, non-breast-feeding women may be enrolled if they are considered highly unlikely to conceive.

Highly unlikely to conceive is defined as:

- 1) surgically sterilized, or
- 2) postmenopausal [postmenopausal is defined as 12 months of amenorrhea in a woman over age 45 years in the absence of other biological or physiological causes; women under the age of 55 years must have a serum follicle stimulating hormone (FSH) level > 40 mIU/mL to confirm menopause], or
- 3) not heterosexually active for the duration of the study, or
- 4) heterosexually active and willing to use 2 methods of birth control (which is

A Phase I/II trial of combination immunotherapy with nivolumab and a CCR2/CCR5 dual antagonist (BMS-813160) with or without GVAX following chemotherapy and radiotherapy for locally advanced pancreatic ductal adenocarcinomas (PDACs)

also required for the female partners of male patients).

Women of childbearing potential must use one of the highly effective methods of contraception (which have a failure rate of < 1% when used consistently and correctly) listed here during study duration and until the end of relevant systemic exposure, starting with Visit 1 through 5 months after the end of study treatment. Approved contraceptive methods include combined (estrogen- and progestogen-containing) hormonal contraception (oral, intravaginal, transdermal), progestogen-only hormonal contraception (oral, injectable), implantable progestogen-only hormonal contraception, other hormonal methods of contraception (vaginal ring, injectables, implants and intrauterine hormone-releasing system), intrauterine device and bilateral tubal occlusion.

A vasectomized partner is a highly effective contraception method provided that the partner is the sole male sexual partner of the WOCBP and the absence of sperm has been confirmed. If not, an additional highly effective method of contraception should be used.

Sexual abstinence is considered a highly effective method only if defined as refraining from heterosexual intercourse during the entire period of risk associated with the study drug. The reliability of sexual abstinence needs to be evaluated in relation to the duration of the study and the preferred and usual lifestyle of the participant. It is not necessary to use any other method of contraception when complete abstinence is elected. WOCBP participants who choose complete abstinence must continue to have pregnancy tests. Acceptable alternate methods of highly effective contraception must be discussed in the event that the WOCBP participants chooses to forego complete abstinence.

The following are unacceptable methods of contraception:

- Male or female condom with or without spermicide. Male and female condoms cannot be used simultaneously
- Diaphragm with spermicide
- Cervical cap with spermicide
- Vaginal Sponge with spermicide
- Progestogen-only oral hormonal contraception, where inhibition of ovulation is not the primary mechanism of action
- Periodic abstinence (calendar, symptothermal, post-ovulation methods)
- Withdrawal (coitus interruptus).
- Spermicide only
- Lactation amenorrhea method (LAM)

Male participants with female partners of childbearing potential are eligible to participate if they agree to the following during the treatment and until the end of relevant systemic exposure:

A Phase I/II trial of combination immunotherapy with nivolumab and a CCR2/CCR5 dual antagonist (BMS-813160) with or without GVAX following chemotherapy and radiotherapy for locally advanced pancreatic ductal adenocarcinomas (PDACs)

- Inform any and all partner(s) of their participation in a clinical drug study and the need to comply with contraception instructions as directed by the investigator.
- Male participants are required to use a condom for study duration and until end of relevant systemic exposure defined as 7 months after the end of study treatment.
- Female partners of males participating in the study to consider use of effective methods of contraception until the end of relevant systemic exposure, defined as 7 months after the end of treatment in the male participant.
- Male participants with a pregnant or breastfeeding partner must agree to remain abstinent from penile vaginal intercourse or use a male condom during each episode of penile penetration during the treatment and until 7 months after the end of study treatment.
- Refrain from donating sperm for the duration of the study treatment and until 7 months after the end of study treatment.
- Confirmed azoospermic males are exempt from contraceptive requirements.

Patients should be informed that taking the study medication may involve unknown risks to the fetus (unborn baby) if pregnancy were to occur during the study. In order to participate in the study they must adhere to the contraception requirement (described above) for the duration of the study. If there is any question that a patient will not reliably comply with the requirements for contraception, that patient should not be entered into the study.

4.5.2 Use in Pregnancy

The investigational agents may have adverse effects on a fetus; therefore, women with a positive pregnancy test at screening will not be eligible for enrollment. If a patient inadvertently becomes pregnant while on treatment with combination immunotherapy or may have been pregnant at the time of investigational product exposure, including during at least 5 half-lives after study drug administration, the patient will immediately be removed from the study. The IND Sponsor and [REDACTED] will be notified immediately via either the CIOMS, MedWatch or appropriate Pregnancy Surveillance Form in accordance with SAE reporting procedures. Protocol-required procedures for study discontinuation and follow-up must be performed on the participant.

The study site will contact the patient at least monthly and document the patient's status until the pregnancy has been completed or terminated. Follow-up information regarding the course of the pregnancy, including perinatal and neonatal outcome and, where applicable, offspring information will be reported on the CIOMS, MedWatch, BMS Pregnancy Surveillance Form, or approved site SAE form. A BMS Pregnancy Surveillance Form may be provided to the study site upon request. The outcome of the pregnancy will also be reported to the IND Sponsor.

A Phase I/II trial of combination immunotherapy with nivolumab and a CCR2/CCR5 dual antagonist (BMS-813160) with or without GVAX following chemotherapy and radiotherapy for locally advanced pancreatic ductal adenocarcinomas (PDACs)

The outcome must be reported to the IND Sponsor within 24 hours [REDACTED] if the outcome is a serious adverse experience (e.g., death, abortion, congenital anomaly, or other disabling or life-threatening complication to the mother or newborn).

Any pregnancy that occurs in a female partner of a male study participant should be reported to BMS. Information on this pregnancy will be collected on the Pregnancy Surveillance Form. In order for BMS, IND Sponsor or designee to collect any pregnancy surveillance information from the female partner, the female partner must sign an informed consent form for disclosure of this information.

4.5.3 Use in Nursing Women

It is unknown whether the investigational agents are excreted in human milk. Since many drugs are excreted in human milk, and because of the potential for serious adverse reactions in the nursing infant, patients who are breast-feeding are not eligible for enrollment.

4.6 Dose Limiting Toxicity

Dose limiting toxicities (DLTs) will be defined based on the incidence, duration and grade of AEs for which no alternate cause can be identified. Adverse events will be evaluated according to the NCI CTCAE v5.0. Every attempt must be made to assign relationship to BMS-813160, nivolumab and/or GVAX. Also, to meet criteria for dose limiting, AEs have to be related to study treatment, not be related to disease progression, be clinically relevant, and be a clinically relevant shift from baseline. DLTs will be assessed in the first cycle of Phase I (starting Cycle 1 Day 1 through prior to initiation of Cycle 2).

Unexpected Grade 3 or greater laboratory abnormalities should be repeated within 24-72 hours if clinically indicated and monitored as necessary to determine if event meets toxicity criteria.

Dose limiting toxicities can include the following AEs (meeting the preceding criteria):

1) Hepatic DLT

- a) Any \geq Grade 3 elevation of AST, ALT, or total bilirubin
- b) Grade 2 AST or ALT with symptomatic liver inflammation (e.g. right upper quadrant tenderness, jaundice, pruritus)
- c) Potential drug induced liver injury (DILI), which is defined as:
 - i. AST or ALT $> 3 \times$ ULN
 - AND
 - ii. Concurrent total bilirubin $> 2 \times$ ULN without initial findings of cholestasis (elevated serum alkaline phosphatase, e.g. findings

A Phase I/II trial of combination immunotherapy with nivolumab and a CCR2/CCR5 dual antagonist (BMS-813160) with or without GVAX following chemotherapy and radiotherapy for locally advanced pancreatic ductal adenocarcinomas (PDACs)

consistent with Hy's law or FDA definition of potential drug-induced liver injury [DILI]) (Note that this special category of DLT uses ULN rather than Common Toxicity Criteria Grade for definition.)

AND

- iii. No other immediately apparent possible causes of transaminase elevation and hyperbilirubinemia, including, but not limited to, viral hepatitis, pre-existing chronic or acute liver disease, or the administration of other drug(s) known to be hepatotoxic.

2) Hematologic DLT

- a) Grade 4 neutropenia ≥ 7 days in duration
- b) Grade 4 lymphopenia ≥ 7 days in duration
- c) Grade 4 thrombocytopenia or Grade 3 thrombocytopenia with bleeding, or any requirement for platelet transfusion
- d) Grade ≥ 3 febrile neutropenia
- e) Grade ≥ 3 hemolysis (i.e. requiring transfusion or medical intervention such as steroids)
- f) Grade 4 anemia not explained by underlying disease

3) Nonhepatic Nonhematologic DLT

- a) Grade 2 or greater episcleritis, uveitis, or iritis
- b) Any other Grade 2 eye pain or blurred vision that does not respond to topical therapy and does not improve to Grade 1 severity within 2 weeks OR requires systemic treatment
- c) Grade 2 myocarditis
- d) Grade 3 pneumonitis, bronchospasm, or neurologic toxicity requires discontinuation
- e) Any Grade 3 or greater nondermatologic, nonhepatic, nonhematologic toxicity will be considered a DLT with the following specific EXCEPTIONS:
 - i. Grade 3 electrolyte or laboratory abnormalities that are not complicated by associated clinical adverse experiences, last less than 48 hours and either resolve spontaneously or respond to conventional medical intervention
 - ii. Grade 3 or 4 elevation of amylase or lipase not associated with clinical or radiographic evidence of pancreatitis
 - iii. Grade 3 nausea, vomiting, or diarrhea that lasts less than 48 hours and either resolves spontaneously or responds to conventional medical intervention
 - iv. Isolated Grade 3 fever not associated with hemodynamic compromise (e.g. hypotension, clinical or laboratory evidence of impaired end-organ perfusion)
 - v. Grade 3 endocrinopathy that is well-controlled by hormone replacement
 - vi. Grade 3 tumor flare (defined as pain, irritation, or rash that localizes to site of known or suspected tumor)

A Phase I/II trial of combination immunotherapy with nivolumab and a CCR2/CCR5 dual antagonist (BMS-813160) with or without GVAX following chemotherapy and radiotherapy for locally advanced pancreatic ductal adenocarcinomas (PDACs)

- vii. Grade 3 fatigue
- viii. Grade 3 infusion reaction that returns to Grade 1 in less than 6 hours as long as vasopressors or epinephrine were not required

4) Dermatologic DLT

- a) Grade 3 rash if no improvement (ie, resolution to \leq Grade 1) after a 1- to 2-week dosing delay
- b) Grade 4 rash of any duration

4.7 Unacceptable Toxicities

Unacceptable toxicities will be used to monitor safety from Cycle 2 Day 1 of Phase I through to end of study treatment and from Cycle 1 Day 1 of Phase II through to end of treatment (see **Section 4.8** for stopping rules). Adverse events will be evaluated according to the NCI CTCAE v5.0.

Unexpected Grade 3 or greater laboratory abnormalities should be repeated within 24-72 hours if clinically indicated and monitored as necessary to determine if event meets toxicity criteria.

Unacceptable toxicities are defined as:

- 1) Treatment-related \geq grade 4 AEs; however, an EXCEPTION may be made for the following upon consultation between the Principal Investigator, IND Sponsor and BMS:
 - a) Grade 4 electrolyte abnormalities < 72 hours in duration
 - b) Grade 4 neutropenia < 7 days in duration
 - c) Grade 4 lymphopenia < 7 days in duration
 - d) Grade 4 increase in amylase or lipase that is not associated with clinical or radiographic evidence of pancreatitis
 - e) Grade 4 hyperglycemia where symptoms are controlled on hormone replacement therapy
- 2) Treatment-related grade 3 AEs, EXCEPT:
 - a) Grade 3 electrolyte or laboratory abnormalities that are not complicated by associated clinical adverse experiences, last less than 48 hours and either resolve spontaneously or respond to conventional medical intervention
 - b) Grade 3 elevation of amylase or lipase not associated with clinical or radiographic evidence of pancreatitis
 - c) Grade 3 nausea, vomiting, or diarrhea that lasts less than 48 hours and either resolves spontaneously or responds to conventional medical intervention
 - d) Grade 3 thrombocytopenia WITHOUT bleeding, or any requirement for platelet transfusion
 - e) Isolated Grade 3 fever not associated with hemodynamic compromise (e.g. hypotension, clinical or laboratory evidence of impaired end-organ perfusion)
 - f) Grade 3 endocrinopathy that is well-controlled by hormone replacement

A Phase I/II trial of combination immunotherapy with nivolumab and a CCR2/CCR5 dual antagonist (BMS-813160) with or without GVAX following chemotherapy and radiotherapy for locally advanced pancreatic ductal adenocarcinomas (PDACs)

- g) Grade 3 tumor flare (defined as pain, irritation, or rash that localizes to site of known or suspected tumor)
 - h) Grade 3 fatigue
 - i) Grade 3 infusion reaction that returns to Grade 1 in less than 6 hours as long as vasopressors or epinephrine were not required
 - j) Grade 3 dermatologic AEs that improves (i.e., resolution to \leq Grade 1) after a 1- to 2-week dosing delay.
- 3) Grade 2 or greater episcleritis, uveitis, or iritis
 - 4) Any other Grade 2 eye pain or blurred vision that does not respond to topical therapy and does not improve to Grade 1 severity within 2 weeks OR requires systemic treatment
 - 5) Potential DILI (defined in **section 4.6**)

4.8 Stopping Rules

We will be monitoring toxicity for each arm in the Phase II portion, and if we observe >33% unacceptable toxicities in any arm, we will halt the enrollment pending safety evaluations and consideration by Principal Investigator, IND Sponsor, BMS and Medical Expert Committee (MEC).

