The Phase II portion is a randomized two-arm study to evaluate immune response, efficacy and safety of the combination of nivolumab and CCR2/CCR5 dual-antagonist (BMS-813160) with and without GVAX. We will be monitoring the toxicities for each arm in the Phase II portion, and if we observe >33% unacceptable toxicities in the first 6 patients or any time afterwards in any arm, we will halt the enrollment pending safety evaluations.

DLTs will be assessed in the first cycle of Phase I, starting Cycle 1 Day 1 through prior to initiation of Cycle 2. Unacceptable toxicities will be used to monitor safety from Cycle 2 Day 1 of Phase I through to end of study treatment and from Cycle 1 Day 1 of Phase II through to end of treatment. During periods of standard of care treatment (FOLFIRINOX-based chemotherapy, SBRT, Surgery) only AEs considered related to study treatment will be collected. If patients develop adverse events (AEs) to any of the three immunotherapies

A Phase I/II trial of combination immunotherapy with nivolumab and a CCR2/CCR5 dual antagonist (BMS-813160) with or without GVAX following chemotherapy and radiotherapy for locally advanced pancreatic ductal adenocarcinomas (PDACs)

(BMS-813160, nivolumab or GVAX) leading to its/their discontinuation, they will be taken off the trial.

All patients will undergo standard of care evaluations consisting of history and physical, CT of the chest/abdomen/pelvis or MRI abd/pelvis and non-contrast CT chest (if do not tolerate contrast) to evaluate for local progression and metastatic disease while they are on study.

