12.2 Sample Size/Accrual Rate

Each year, approximately 250 patients with newly diagnosed locally advanced pancreatic cancer are seen at JHH. Approximately, 50% of these patients will potentially be enrolled in clinical trials.

Phase I: 3-12 patients (3+3 design with Nivo+GVAX+BMS-813160 at two dose levels, primary endpoint - safety).

Phase II: up to 15 patients (primary endpoint - immunologic)

The first 10 patients will be randomized 1:1 into two arms:

Arm A: *nivolumab*+ *BMS-813160*

Arm B: *nivolumab*+ *BMS-813160*+ *GVAX*

Up to 5 additional patients will be assigned to Arm C: *nivolumab* + *BMS-813160* in Cycle 1

Due to the availability of BMS-813160, the enrollment of Phase II Arm A and Arm B will close early before full accrual under the original protocol. An amendment is required to change the design of the phase II portion. The analysis plan is also changed accordingly. The primary endpoint remains to be immunologic response, defined in Section 12.1 above.

The analysis will be performed separately in two groups of patients receiving either *nivolumab*+ *BMS-813160* (Group 1), or *nivolumab*+ *BMS-813160*+ *GVAX* (Group 2). Group 2 will include patients treated with the triplet regimen at the RP2D during both Phase II and Phase I portion. We expect up to 10 patients in Group 2 (including 6 treated at the 300mg dose in Phase I and 5 patients in Arm B of Phase II). A rate of immune response of 5% or lower is not considered worthy of further investigation, whereas immune response rate of at least 30% is consider worthy of further study.

Group 1 will have 8, up to 10, patients treated with the doublet regimen during Phase II (including up to 5 patients in Arm A and 3 to 5 patients anticipated to be enrolled to Arm C who receive *nivolumab* + *BMS-813160* in Cycle 1 and *nivolumab* + *GVAX* from Cycle 2 and after). It allows us to make preliminary assessment of immune response.

The probability of events under different true immune response rate is as follow:

number of responders out of 8 patients	True response rate				
	0.3	0.25	0.2	0.1	0.05
>=1	0.943	0.900	0.832	0.570	0.337
>=2	0.745	0.633	0.497	0.187	0.057
>=3	0.448	0.321	0.203	0.038	0.006
number of responders out of 10 patients					
	0.3	0.25	0.2	0.1	0.05
>=1	0.972	0.944	0.893	0.651	0.401
>=2	0.851	0.756	0.624	0.264	0.086
>=3	0.617	0.474	0.322	0.070	0.012

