12.5 Analysis of Secondary Endpoints – Phase II Safety Assessment

The safety analysis will be performed in all treated subjects. AE data will be listed individually and incidence of AEs summarized by system organ class and preferred terms within a system organ class for each treatment group. When calculating the incidence of AEs, each AE (based on preferred terminology defined by CTCAE version 5.0) will be counted only once for a given subject. In analyses of grade and causality, if the same AE occurs on multiple occasions, the highest grade and strongest relationship to study drug will be assumed. If 2 or more AEs are reported as a unit, the individual terms will be reported as separate experiences.

Changes in vital signs, hematology and clinical chemistry parameters from baseline to the end of the study will be examined. Toxicity will be tabulated by type and grade. Toxicities will be characterized according to the CTCAE version 5.0. Treatment-emergent changes from normal to abnormal values in key laboratory parameters will be identified.

We will monitor adverse events in phase II, and if we observe >33% unacceptable toxicities in the first 6 patients or any time afterwards in any arm, we will halt the enrollment pending safety evaluations. Specifically, we stop if:

Number of patients in the same arm with AE \geq	2	3
In number of patients in that arm between	2-6	7 - 9

The operating characteristics of the stopping rule for toxicity are shown below and are based on 5000 simulations:

Risk of AE	0.10	0.20	0.25	0.30	0.33	0.40	0.45
% of Time study stops	12.2%	37.8%	52.8%	65.3%	71.6%	83.7%	89.8%
Expected sample size	8.66	7.98	7.57	7.21	7.03	6.66	6.45

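### The Section 12.5 toxicity stopping table describes a 9-patient arm, but no amended Phase II arm exceeds 5 patients, so its stopping probabilities are too high

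*Combined protocol and SAP*

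**What the plan says.** The >33% rule appears in three places. Section 4.8 states it as "We will be monitoring toxicity for each arm in the Phase II portion, and if we observe >33% unacceptable toxicities in any arm", with a halt in enrollment pending review. Section 1.7 limits it the same way: "We will be monitoring the toxicities for each arm in the Phase II portion". Section 12.5 repeats it and adds a boundary whose first row is headed "Number of patients in the same arm with AE": at least 2 when 2 to 6 patients have been treated, at least 3 when 7 to 9 have. Sections 1.7 and 12.5 also speak of the first 6 patients or any later time; Section 4.8 sets no minimum.

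Section 12.5 then says "The operating characteristics of the stopping rule for toxicity are shown below and are based on 5000 simulations" and tabulates seven risks from 0.10 to 0.45.

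Section 12.2, rewritten when BMS-813160 became unavailable, sets Phase II at up to 15 patients: 10 randomized 1:1 to Arms A and B, and up to 5 assigned to Arm C, with 3 to 5 anticipated there.

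On Phase I, Section 4.6 says "DLTs will be assessed in the first cycle of Phase I (starting Cycle 1 Day 1 through prior to initiation of Cycle 2" begins. Section 4.7 takes over from there: "Unacceptable toxicities will be used to monitor safety from Cycle 2 Day 1 of Phase I through to end of study treatment". Section 12.2 pools some of these patients with Arm B for the immune endpoint: "Group 2 will include patients treated with the triplet regimen at the RP2D during both Phase II and Phase I portion", described as "including 6 treated at the 300mg dose in Phase I and 5 patients in Arm B of Phase II".

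**The concern.** Operating characteristics tell investigators and the DSMB how likely a rule is to catch an unsafe regimen. The amendment changed the size of the arms, but the table still shows expected sample sizes larger than any arm can be. A reader relying on it would think an arm with a true unacceptable-toxicity risk of one third has about a 72% chance of triggering review.

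A secondary question is what stands behind unacceptable toxicity as the Phase I monitor after Cycle 1, since every statement of the numeric rule is confined to Phase II arms.

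**Working it through.** **Inputs.** Boundary, risks and stated figures: Section 12.5. Arm sizes: Section 12.2. Patients are taken as independent with common risk p; q = 1 − p.

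**Reproducing the plan's table (9 patients).** Let X be the number of events in the first 6 patients.

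- Stop = P(X ≥ 2) + P(X = 1)·P(at least 2 of 3) + P(X = 0)·p³.
- Expected N, first check at patient 6 = 6·P(X ≥ 2) + 8·P(X = 1)·p² + 9·(remaining probability).

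At p = 0.33: P(X = 0) = 0.67⁶ = 0.0905; P(X = 1) = 6(0.33)(0.67⁵) = 0.2673; P(X ≥ 2) = 0.6422; P(at least 2 of 3) = 0.2548; p³ = 0.0359.

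- Stop = 0.6422 + 0.2673(0.2548) + 0.0905(0.0359) = 0.714. The plan has 71.6%.
- Expected N = 6(0.6422) + 8(0.2673)(0.1089) + 9(0.3287) = 7.04. The plan has 7.03.

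The stopping probability is the same whether checks begin at patient 2 or patient 6, because a count of 2 reached early still stands at patient 6. Expected N does differ: checks from patient 2 give 5.75 at p = 0.33, against the stated 7.03. A cap of 10 with a first check at 6 gives 7.33. Of the configurations tried (cap 9 or 10; first check at 2 or 6, plus first check at 3 with cap 9), only cap 9 with a first check at 6 matches both rows.

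**The amended arm (5 patients, at least 2 events, checked from patient 2).**

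- Stop = 1 − q⁵ − 5pq⁴.
- Expected N = 5 − 3p² − 4p²q − 3p²q².

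At p = 0.33: stop = 1 − 0.1350 − 0.3325 = 0.532; expected N = 5 − 0.3267 − 0.2919 − 0.1467 = 4.23.

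| Risk | Stop %: plan | Stop %: exact, 9 | Stop %: exact, 5 | E(N): plan | E(N): exact, 9 | E(N): exact, 5 |
|---|---|---|---|---|---|---|
| 0.10 | 12.2 | 12.5 | 8.1 | 8.66 | 8.65 | 4.91 |
| 0.20 | 37.8 | 38.8 | 26.3 | 7.98 | 7.95 | 4.68 |
| 0.25 | 52.8 | 52.4 | 36.7 | 7.57 | 7.58 | 4.52 |
| 0.30 | 65.3 | 64.8 | 47.2 | 7.21 | 7.23 | 4.35 |
| 0.33 | 71.6 | 71.4 | 53.2 | 7.03 | 7.04 | 4.23 |
| 0.40 | 83.7 | 83.5 | 66.3 | 6.66 | 6.67 | 3.96 |
| 0.45 | 89.8 | 89.7 | 74.4 | 6.45 | 6.46 | 3.76 |

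The overstatement runs from 12.2 − 8.1 = 4.1 points at risk 0.10 to 71.6 − 53.2 = 18.4 points at 0.33.

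Arm C may be smaller still. At p = 0.33, 4 patients give 1 − 0.67⁴ − 4(0.33)(0.67³) = 40.1%, and 3 patients give 25.5% (the 0.2548 above).

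**Phase I, side by side.** Section 4.7 names unacceptable toxicity as the Phase I monitor from Cycle 2. Sections 1.7, 4.8 and 12.5 attach the number to Phase II arms. The only numeric Phase I rule is the 3+3 in Section 1.7, limited to first-cycle DLTs. For example, 3 of 6 Phase I patients at 300 mg after Cycle 1 plus 1 of 5 in Arm B is 4/11 = 36% on one regimen, yet no count is crossed: Arm B stands at 1 event.

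**The case against.** The strongest objection is practical. The rule's stated action is to halt enrollment, and enrollment closed on 19 December 2022, so a mislabelled table changes little. That stands as to consequence. It does not make the table right: Section 12.5 still presents it as the rule's current performance, and patients already enrolled but not yet randomized go on to start treatment in Arm C.

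Two stronger readings are tempting.

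- A reader might infer that a 5-patient arm is never checked, because the expected sizes imply a first look at patient 6. The documents do not support this. The boundary row begins at 2 patients and Section 4.8 sets no minimum. The wording about the first 6 patients is ambiguous, and the expected-size row reflects how the simulation was run.
- A reader might infer that Phase I triplet patients are unmonitored after Cycle 1 and need a trigger pooled with Arm B. They are monitored: individual removal (4.9), SAE reporting within 24 hours (6.5), weekly meetings and monthly calls (11.2), and SMC and DSMB review (11.3) all apply, and Sections 12.3 and 12.5 report harm in all treated subjects. The pointer to 4.8 in Section 4.7 follows the Phase II clause, so it need not promise a Phase I rule. A 3+3 with no later numeric trigger is a defensible design. Pooling for the immune endpoint does not oblige pooling for stopping.

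A pooled trigger would also perform poorly. Suppose the boundary is extended to 4 in 10–11, Arm B's own count is kept, and 3 to 6 Phase I patients contribute. Run sequentially at equal risk, it alerts 43–52% of the time at a risk of 0.20. Counted once, with Phase I risk half of Arm B's, it alerts 54–58% at an Arm B risk of 0.33, only about 1 to 5 points above Arm B alone. A single tally of 3/6 plus 0/5 is 3/11, below the boundary.

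**Conclusion.** The Section 12.5 operating characteristics do not describe the amended design. They belong to a 9-patient arm first checked at patient 6. For a 5-patient arm the true stopping probabilities are 4 to 18 points lower, the 7–9 row cannot be reached, and every stated expected size is impossible. The 9-patient basis is inferred from reproducing both rows; the plan does not state it. The 5-patient figures assume independent patients, a full arm of 5, and checks from patient 2. The importance is minor because enrollment is closed.

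The Phase I point is secondary. It is true that no numeric group-level trigger covers 300 mg Phase I patients after the DLT window. The documents do not show that this left them without oversight, nor that any of them is still on treatment.

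**What to change.** In Section 12.5, replace the table with the 5-patient figures above: stop 8.1 / 26.3 / 36.7 / 47.2 / 53.2 / 66.3 / 74.4%, and expected N about 4.9 / 4.7 / 4.5 / 4.3 / 4.2 / 4.0 / 3.8. If the existing figures are kept for the record, label them as computed for a 9-patient arm. In Sections 1.7 and 12.5, remove any suggestion that checking waits for patient 6, and say that the count of 2 governs. Otherwise the percentage wording would trigger on one event among 2 or 3 patients (50% or 33.3%). The cost is one recalculated table and a few words; no simulation, visits or patients are needed.

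Optionally, tabulate the unacceptable-toxicity proportion in Group 2 from Cycle 2 onward with an exact 95% interval, beside the Group 2 immune-response rate. State that safety uses all treated subjects, while the immune endpoint uses those who completed one cycle. Section 4.7 already applies the definition to both parts of Group 2 in that period, so Phase I Cycle 1 events need no re-adjudication. The interval will be wide: 4 of 11, for example, gives 10.9–69.2%. The denominator also needs stating, since Section 12.2 says up to 10 in Group 2 while its components sum to 6 + 5 = 11. No new pooled stopping trigger is recommended.
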